6.9.2 Safety analyses

All patients who initiate study treatment will be evaluated for safety, combined across both cohorts. Adverse events will be summarized as number (%) of patients by system organ class, CTCA term and grade, where grade is the maximum across a patient's treatment period.

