5.11.1 Procedures for discontinuation of study treatment

The investigator should instruct the patient to contact the site before or at the time if Study treatment is stopped. A patient that decides to discontinue Study treatment will always be asked about the reason(s) and the presence of any AEs. The date of last intake of Study treatment should be documented in the CRF (electronic or paper). All Study treatment should be returned by the patient at their next on-site study visit or unscheduled visit. Patients permanently discontinuing Study treatment should be given locally available standard of care therapy, at the discretion of the Investigator.

Any patient discontinuing investigational product should be seen post discontinuation for the evaluations and sample collections outlined in the study schedule.

After discontinuation of the study medication at any point in the study, all ongoing AEs or SAEs must be followed until resolution unless, in the Investigator's opinion the condition is unlikely to resolve due to the patients underlying disease, or the patient is lost to follow up (see Section 5.12) All new AEs and SAEs occurring during the 30 calendar days after the last dose of study medication must be reported (if SAEs, they must be reported within 24 hours as described in Section 6.4.2) and followed to resolution as above. Patients should be seen within 30 days after discontinuing study medication to collect and / or complete AE information. For guidance on reporting adverse events after the 30 day follow up period see Section 6.4.2.1.

Discontinuation of Study treatment, for any reason, does not impact on the patient's participation in the study. The patient should continue attending subsequent study visits and data collection should continue according to the study protocol. If the patient does not agree to continue in-person study visits, a modified follow-up must be arranged to ensure the collection of endpoints

and safety information. This could be a telephone contact with the patient, a contact with a relative or treating physician, or information from medical records. The approach taken should be recorded in the medical records. A patient that agrees to modified follow-up is not considered to have withdrawn consent or to have withdrawn from the study.

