6.4.2 Time period and frequency for collecting AE and SAE information

Adverse Events will be collected from time of enrolment throughout the treatment period and including the follow-up period until last contact.

SAEs will be recorded from the time of signing of informed consent form.

All SAEs will be recorded and reported to the sponsor or designee within 24 hours, as indicated in Appendix B. The investigator will submit any updated SAE data to the sponsor within 24 hours of it being available.

Investigators are not obligated to actively seek AE or SAE in former study patients. However, if the investigator learns of any SAE, including a death, at any time after a patient's last visit and he/she considers the event to be reasonably related to the Study treatment or study participation, the investigator may notify the sponsor.

The method of recording, evaluating, and assessing causality of AE and SAE and the procedures for completing and transmitting SAE reports are provided in Appendix B.

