6.4.2.1 Adverse events after the end of treatment visit

For Pharmacovigilance purposes and characterization, any SAE of MDS/AML or new primary malignancy occurring after end of treatment should be reported to AstraZeneca Patient Safety regardless of investigator's assessment of causality or knowledge of the treatment arm. Investigators will be asked during the regular follow up for overall survival if the patient has developed MDS/AML or a new primary malignancy and prompted to report any such cases.

At any time after a patient has completed the study, if an Investigator learns of any SAE including sudden death of unknown cause, and he/she considers there is a reasonable possibility that the event is causally related to the investigational product, the investigator should notify AstraZeneca, Patient Safety.

If patients who are gaining clinical benefit are allowed to continue study treatment post data cut off and/or post study completion then all SAEs must continue to be collected and reported to Patient Safety within the usual timeframe.

Otherwise, after study treatment completion (i.e. after any scheduled post treatment follow-up period has ended) there is no obligation to actively report information on new AEs or SAEs occurring in former study patients. This includes new AEs/SAEs in patients still being followed up for survival but who have completed their end of treatment visit.

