6.4.12 Deaths

All deaths that occur during the study, or within the protocol-defined 30-day post-study follow-up period after the administration of the last dose of study treatment, must be reported as follows:

- Death clearly the result of disease progression should be reported to the study monitor at the next monitoring visit and should be documented in the CRF but should not be reported as an SAE.
- Where death is not due (or not clearly due) to progression of the disease under study, the AE causing the death must be reported to the study monitor as a SAE within **24 hours** (see Section 8.4.1 for further details). The report should contain a comment regarding the co-involvement of progression of disease, if appropriate, and should assign main and contributory causes of death. This information can be captured in the CRF.

Deaths with an unknown cause should always be reported as a SAE. A postmortem maybe helpful in the assessment of the cause of death, and if performed a copy of the post-mortem results should be forwarded to AstraZeneca within the usual timeframes.

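### Section 6.9.2 takes maximum AE grade over the treatment period, so events that start or worsen in the mandatory 30-day reporting window after the last dose have no clear place in the safety summary

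*Combined protocol and SAP*

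**What the plan says.** Section 6.9.2 is the whole safety analysis plan. The population is clear: "All patients who initiate study treatment will be evaluated for safety, combined across both cohorts". AEs are then counted by system organ class, term and grade, where "grade is the maximum across a patient's treatment period". The section gives no window after the last dose, no definition of a treatment-emergent event and no listing of later events.

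The collection rules reach further:

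- Section 5.11.1: "All new AEs and SAEs occurring during the 30 calendar days after the last dose of study medication must be reported". It adds: "Patients should be seen within 30 days after discontinuing study medication to collect and / or complete AE information".
- Section 6.4.2: "Adverse Events will be collected from time of enrolment throughout the treatment period and including the follow-up period until last contact".
- Section 6.4.12 has deaths reported during the study or "within the protocol-defined 30-day post-study follow-up period after the administration of the last dose of study treatment".
- Section 6.4.2.1: "any SAE of MDS/AML or new primary malignancy occurring after end of treatment should be reported". For other new events it removes the duty to report actively once scheduled post-treatment follow-up is over, and it extends this to men in survival follow-up who have had their end-of-treatment visit.

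The secondary objective in section 3.2 is the incidence and severity of AEs. It is not restricted to time on drug.

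**The concern.** The analysis window and the collection window do not match. The protocol makes sites report new AEs for 30 days after the last dose and schedules a visit for it, but the only tabulation rule refers to a period that, in the protocol's own vocabulary, comes before follow-up. An analyst who applies 6.9.2 as worded would give post-dose events no grade and would freeze ongoing events at their worst grade on drug. Another analyst might extend the period to the end-of-treatment visit and produce a different table from the same data.

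At stake are the reported incidence and maximum grade in the safety endpoint, and whether late cases of MDS/AML or a new primary malignancy, both named as events of special interest in section 6.4.13, appear in the trial's own safety results.

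**Working it through.** The plan gives no figure on this point to reproduce. The check compares the windows and then does one piece of arithmetic on scale.

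**Step 1. The windows side by side**

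| Place | What it governs | Reach after the last dose |
|---|---|---|
| 6.9.2 | Grade in the AE summary | None stated; treatment period |
| 5.11.1 | Reporting of new AEs and SAEs | 30 calendar days |
| Schedule of Activities; 5.11.1 | End-of-treatment AE review | One visit, within 30 days |
| 6.4.2 | AE collection | Follow-up, to last contact |
| 6.4.12 | Reporting of deaths | 30 days, called follow-up |
| 6.4.2.1 | MDS/AML, new primary malignancy | After end of treatment, no end date given |
| 6.4.2.1 | Other new AEs | No active duty after scheduled follow-up or the end-of-treatment visit |

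**Step 2. What the treatment period means.** No section defines it. Section 6.4.2 lists it next to the follow-up period as a separate item. Section 5.11.1, Table 4 and section 6.4.12 all call the 30 days after the last dose follow-up. The literal reading is therefore that the treatment period stops at the last dose.

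**Step 3. Apply the grade rule to three kinds of event**

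- An AE that starts after the last dose, within 30 days: reported under 5.11.1, but it has no grade within the treatment period and so no stated grade cell.
- An AE that starts on drug and worsens after the last dose: counted, but at the lower on-treatment grade.
- MDS/AML or a new primary malignancy after end of treatment: reported under 6.4.2.1, with no stated place in 6.9.2. Section 6.5.5.1 shows how this can arise. Hematology referral comes when counts are still abnormal after 4 weeks of interruption, with marrow analysis considered then. If dosing never resumes, that is 4 × 7 = 28 days or more after the last dose.

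**Step 4. Scale.** Input: planned enrolment of 30 (section 6.8), taken as the number treated.

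- Shift in a table row per affected patient: 1/30 = 0.033, or 3.3 percentage points.
- The documents give no proportion of patients whose only or worst event of a term falls after the last dose, so a range is assumed. The expected number affected is 30 × q, and the chance of at least one is 1 − (1 − q)^30.

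| Assumed q | Expected patients | Chance of at least one |
|---|---|---|
| 2% | 0.6 | 1 − 0.98^30 = 45% |
| 5% | 1.5 | 1 − 0.95^30 = 79% |
| 10% | 3.0 | 1 − 0.90^30 = 96% |

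The 3.3 points follow from the plan. The second table shows only how the result depends on an unknown rate.

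**The case against.** The strongest reply is that 6.9.2 excludes nothing. Its statement that AEs will be summarized carries no time limit; the treatment period appears only in the clause defining grade, which is a rule for counting each patient once at worst grade. The period is also undefined, and a wider reading has some support: section 6.4.2.1 explains completion of study treatment as the end of any scheduled post-treatment follow-up, and the Schedule of Activities includes AE review at the end-of-treatment visit. This stands to the extent that a reader might infer that post-dose events are barred from every table, and the documents do not say so. It does not remove the problem. The gloss in 6.4.2.1 concerns a different term, and a summary by grade still needs a grade for each event.

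A second reply is that on-treatment emphasis is reasonable. Patients stop at progression and may go on to standard therapy, so events in the next 30 days need not reflect olaparib, and with one arm no between-arm comparison can be distorted. That is fair. A reader might also infer that events around stopping are the ones most likely to be toxicity; nothing in the documents supports that. An AE that itself causes the stop begins on drug and is already counted, so at most its later worsening is lost.

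Third, late MDS/AML and malignancy reports go to the manufacturer's safety group for pharmacovigilance. That explains why they are collected, but it does not tell the analyst whether to show them.

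Fourth, 30-day reporting and collection to last contact can coexist as a minimum and a broader rule. They can, but collection to last contact and no active duty after the end-of-treatment visit are harder to combine.

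**Conclusion.** The point holds as a mismatch between what is collected and what 6.9.2 says will be graded. Read literally, AEs starting after the last dose have no stated grade, AEs worsening after it are shown too low, and late MDS/AML and new primary malignancies have no stated place in the safety analysis. Each affected patient shifts a row by 3.3 percentage points, assuming all 30 planned patients are treated. How many patients are affected cannot be estimated from the documents.

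Three larger claims are tempting and should not be made:

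- That pneumonitis shares the late-reporting rule. Section 6.4.13 makes it an event of special interest, but the late duty in 6.4.2.1 names only MDS/AML and new primary malignancy.
- That the omitted share can be read from treatment duration. Using the 5.8 and 7.4 month median PFS quoted in section 2.1 gives 1/(5.8 + 1) = 15% and 1/(7.4 + 1) = 12%, but those are medians from another trial, for PFS rather than time on drug, and a share of time is not a share of events.
- That ascertainment is known to differ between patients. The conflicting windows allow it; nothing shows its extent.

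The matter is minor. It touches a descriptive secondary endpoint and leaves the primary analysis and sample size unchanged.

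**What to change.** In section 6.9.2, state that AEs are summarized, and maximum grade taken, from first dose to 30 days after the last dose, in line with 5.11.1. Add a listing of all MDS/AML and new primary malignancies whenever they are reported, with time from last dose.

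Reconcile the AE collection windows in 5.11.1 (30 days), 6.4.2 (until last contact) and 6.4.2.1 (no obligation after the end-of-treatment visit), so that it is clear what is sought from a man whose end-of-treatment visit falls early in the 30 days. Section 6.4.3 belongs in that reconciliation: it ends CRF recording of unresolved AEs at the last AE assessment, so a later worsening might not reach the database.

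The cost is a few sentences and no new assessments: new events are already reportable for 30 days, and grade changes are already recorded (section 6.4.4, Appendix B 6). The downside is slightly higher AE counts, some of which may reflect progression or subsequent therapy. Showing on-treatment and post-dose events in separate columns would let the reader see that.

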Appendix A Actions required in cases of increases in liver biochemistry and evaluation of Hy's Law

A 1 Introduction

This Appendix describes the process to be followed in order to identify and appropriately report cases of Hy's Law. It is not intended to be a comprehensive guide to the management of elevated liver biochemistries.

During the course of the study the Investigator will remain vigilant for increases in liver biochemistry. The Investigator is responsible for determining whether a patient meets potential Hy's Law (PHL) criteria at any point during the study.

The Investigator participates, together with AstraZeneca clinical project representatives, in review and assessment of cases meeting PHL criteria to agree whether Hy's Law (HL) criteria are met. HL criteria are met if there is no alternative explanation for the elevations in liver biochemistry other than drug induced liver injury (DILI) caused by the investigational medicinal product (IP).

The Investigator is responsible for recording data pertaining to PHL/HL cases and for reporting Adverse Events (AE) and Serious Adverse Events (SAE) according to the outcome of the review and assessment in line with standard safety reporting processes.

A 2 Definitions

Potential Hy's Law (PHL)

Aspartate aminotransferase (AST) or alanine aminotransferase (ALT) $\geq 3 \times$ upper limit of normal (ULN) **together with** total bilirubin (TBL) $\geq 2 \times$ ULN at any point during the study following the start of study medication irrespective of an increase in alkaline phosphatase (ALP).

Hy's Law (HL)

AST or ALT $\geq 3 \times$ ULN **together with** TBL $\geq 2 \times$ ULN, where no other reason, other than the IMP, can be found to explain the combination of increases, eg, elevated ALP indicating cholestasis, viral hepatitis, another drug.

For PHL and HL the elevation in transaminases must precede or be coincident with (ie, on the same day) the elevation in TBL, but there is no specified time frame within which the elevations in transaminases and TBL must occur.

A 3 Identification of potential Hy's Law cases

In order to identify cases of PHL it is important to perform a comprehensive review of laboratory data for any patient who meets any of the following identification criteria in isolation or in combination:

- ALT $\geq 3 \times$ ULN

- $AST \geq 3 \times ULN$
- $TBL \geq 2 \times ULN$

When the identification criteria are met the Investigator will without delay:

- Determine whether the patient meets PHL criteria (see Appendix A 2 for definition) by reviewing laboratory reports from all previous visits
- The Investigator will without delay review each new laboratory report and if the identification criteria are met will:
- Determine whether the patient meets PHL criteria (see Appendix A 2 for definition) by reviewing laboratory reports from all previous visits
- Promptly enter the laboratory data into the laboratory CRF

A 4 Follow-up

A 4.1 Potential Hy's Law criteria not met

If the patient does not meet PHL criteria the Investigator will:

- Perform follow-up on subsequent laboratory results according to the guidance provided in the Clinical Study Protocol.

A 4.2 Potential Hy's Law criteria met

If the patient does meet PHL criteria the Investigator will:

- Monitor the patient until liver biochemistry parameters and appropriate clinical symptoms and signs return to normal or baseline levels, or as long as medically indicated
- Investigate the etiology of the event and perform diagnostic investigations as medically indicated.
- If at any time the PHL case meets serious criteria, report it as an SAE using standard reporting procedures.

A 5 Review and assessment of potential Hy's Law cases

The instructions in this section should be followed for all cases where PHL criteria are met.

If there is an alternative explanation for the ALT or AST and TBL elevations, a determination of whether the alternative explanation is an AE will be made and subsequently whether the AE meets the criteria for a SAE:

- If the alternative explanation is **not** an AE, record the alternative explanation on the appropriate CRF
- If the alternative explanation is an AE/SAE, record the AE /SAE in the CRF accordingly

If there is **no** explanation that would explain the ALT or AST and TBL elevations other than the IMP:

- Report an SAE (report term 'Hy's Law')
 - The 'Medically Important' serious criterion should be used if no other serious criteria apply
 - As there is no alternative explanation for the HL case, a causality assessment of 'related' should be assigned.

If there is an unavoidable delay of over 3 weeks in obtaining the information necessary to assess whether or not the case meets the criteria for HL, then it is assumed that there is no alternative explanation until such time as an informed decision can be made:

- Report an SAE (report term 'Potential Hy's Law') applying serious criteria and causality assessment as per above
- Continue follow-up and review. Once the necessary supplementary information is obtained, repeat the review and assessment to determine whether HL criteria are met. Update the SAE report according to the outcome of the review amending the reported term if an alternative explanation for the liver biochemistry elevations is determined.

A 6 Actions required when potential Hy's Law criteria are met before and after starting study treatment

This section is applicable to patients with liver metastases who meet PHL criteria on Study treatment having previously met PHL criteria at a study visit prior to starting Study treatment.

At the first on-study treatment occurrence of PHL criteria being met, the Investigator will determine if there has been a significant change in the patients' condition[#] compared with the last visit where PHL criteria were met.[#]

- If there is no significant change, no action is required
- If there is a significant change, then follow the subsequent process described in Appendix B 5.
- A 'significant' change in the patient's condition refers to a clinically relevant change in any of the individual liver biochemistry parameters (ALT, AST or total bilirubin) in isolation or in combination, or a clinically relevant change in associated symptoms.

The determination of whether there has been a significant change will be at the discretion of the Investigator.

A 7 Actions required for repeat episodes of potential Hy's Law

This section is applicable when a patient meets PHL criteria on study treatment, and has already met PHL criteria at a previous on study treatment visit.

The requirement to conduct follow-up, review, and assessment of a repeat occurrence(s) of PHL is based on the nature of the alternative cause identified for the previous occurrence.

The investigator should determine the cause for the previous occurrence of PHL criteria being met and answer the following question:

Was the alternative cause for the previous occurrence of PHL criteria being met found to be the disease under study (eg, chronic or progressing malignant disease, severe infection or liver disease), or did the subject meet PHL criteria prior to starting study treatment and at first on-study treatment visit, as described in Appendix A 6?

If **No**: Follow the process described in Appendix A 4.1.

If **Yes**: Determine if there has been a significant[#] change in the patient's condition compared with when PHL criteria were previously met.

If there is no significant change, no action is required.

If there is a significant change, follow the process described in Appendix A 4.

A 'significant' change in the patient's condition refers to a clinically relevant change in any of the individual liver biochemistry parameters (ALT, AST or total bilirubin) in isolation or in combination, or a clinically relevant change in associated symptoms. The determination of whether there has been a significant change will be at the discretion of the Investigator.

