1.0 PROTOCOL SUMMARY

1.1 Schedule of Activities (SoA)

Table 1 Schedule of Activities

Treatment Cycle	Pre-Screening	Screening	Treatment Cycles ^a					End of Treatment
			Cycle 1 ^g	Cycle 2	Cycle 3	Cycle 4	After Cycle 4	
Cycle Day		Day -30 to 0	Day 1 +/- 7 days	Day 1 +/- 7 days	Day 1 +/- 7 days	Day 1 +/- 7 days	Day 1 +/- 7 days	Within 30 days
Administrative Procedures								
Informed Consent		X						
Inclusion/Exclusion Criteria		X						
Demographics and Medical History		X						
Prior and Concomitant Medication Review		X	X	X	X	X	Q1C	X
Olaparib Dispensation			X	X	X	X	Q1C	
Clinical Assessments								
Review Adverse Events			X	X	X	X	Q1C	X
ECOG Performance Status		X	X	X	X	X	Q1C	X
Vital Signs and Weight		X	X	X	X	X	Q1C	X
Physical Examination ^b		X	X	X	X	X	Q1C	X

EKG		X						
Laboratory Assessments								
LOH Assessment	X ^d							
iHRD Analysis/Whole Exome Sequencing		X						
PSA		X	X			X	Q3C	X
Testosterone Level		X						
CBC with Differential		X	X	X	X	X	Q1C	X
Comprehensive Serum Chemistry Panel		X	X	X	X	X	Q1C	X
PT/INR and PTT		X						
Urinalysis		X						
Correlative Studies Blood Collection ^e			X			X		X
Research Biopsy ^e		X						X
Radiographic Assessments ^f		X ⁱ				X	Q3C	

- A. One treatment cycle is equal to 28 days
- B. Full physical exam is required at screening. Subsequent physical exams may be targeted.
- C. Refer to Laboratory Manual for details on correlative blood sample processing.
- D. Pathologic assessment to evaluate LOH score is a pre-screening requirement and will be performed on archival tissue or ctDNA. Sufficient tissue must also be available for whole exome sequencing in order to determine iHRD status.
- E. If archival metastatic tissue previously obtained is already available and suitable for research assessments, another metastatic biopsy will not be mandated. Research biopsy will only occur if considered safe and feasible by the treatment team. CBC with Differential, PT/INR and PTT will only be obtained in the pre-screening period if metastatic biopsy is planned.
- F. Radiographic assessments should include a CT chest/abdomen/pelvis and bone scan. PET/CT or MRI may be used as initial screening assessments.
- G. Assessments done during the screening period do not need to be repeated if within 7 days.
- H. Assessments do not need to be repeated if within 7 days
- I. Radiographic assessments do not need to be repeated if within 8 weeks

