6.3.1 Clinical safety laboratory assessments

Blood samples for determination of clinical chemistry and hematology will be taken at the times indicated in the assessment schedules as clinically indicated (see the SoA). Clinical laboratory safety tests will be performed in a licensed clinical laboratory according to local standard procedures. Sample tubes and sample sizes may vary depending on the laboratory method used and routine practice at the site. Abnormal clinically significant laboratory results should be repeated as soon as possible (preferably within 24 to 48 hours).

Additional safety samples may be collected if clinically indicated at the discretion of the treating physician and sponsor investigator. The date, time of collection, and results (values, units, and reference ranges) will be recorded on the appropriate eCRF.

The laboratory variables to be measured are presented in this section in Table 9.

Table 9 Laboratory safety variables

Hematology/Hemostasis (whole blood)	Clinical Chemistry (serum or plasma)
B-Hemoglobin (Hb)	S/P-Creatinine
B-Leukocyte count	S/P-Bilirubin, total
B-Absolute neutrophil count	S/P-Alkaline phosphatase (ALP)
B-Absolute lymphocyte count	S/P-Aspartate transaminase (AST)
B-Platelet count	S/P-Alanine transaminase (ALT)
B-Mean cell volume (MCV)	S/P-Albumin
	S/P-Potassium
	S/P-Calcium, total
Urinalysis (dipstick)	S/P-Sodium
	S/P- Urea or Blood Urea Nitrogen (BUN)
U-Hb/Erythrocytes/Blood	S/p- Total Protein
U-Protein/Albumin	
U-Glucose	

NB. In case a patient shows an AST **or** ALT $\geq 3 \times \text{ULN}$ together with total bilirubin $\geq 2 \times \text{ULN}$ please refer to Appendix A ‘Actions required in cases of increases in liver biochemistry and evaluation of Hy’s Law’, for further instructions.

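### Appendix A 7 sends some repeat episodes that meet potential Hy's Law criteria to A 4.1, the follow-up meant for patients who do not meet them

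*Combined protocol and SAP*

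**What the plan says.** A 7 sets its own scope, a later on-treatment visit at which the criteria are met again: "This section is applicable when a patient meets PHL criteria on study treatment, and has already met PHL criteria at a previous on study treatment". It then states that the cause found for the earlier episode decides the handling: "The requirement to conduct follow-up, review, and assessment of a repeat occurrence(s) of PHL is based on the nature of the alternative cause identified". The investigator is asked whether that earlier episode was found to be due to the disease under study, or whether the patient had already met PHL criteria before treatment and at the first on-treatment visit, as A 6 describes.

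- If 'No': "Follow the process described in Appendix A 4.1".
- If 'Yes' without a significant change: no action.
- If 'Yes' with a significant change: the process in A 4.

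A 4 has two parts. A 4.1 is for criteria not met and opens "If the patient does not meet PHL criteria the Investigator will", followed by a single action: "Perform follow-up on subsequent laboratory results according to the guidance provided in the Clinical Study Protocol". A 4.2 is for criteria met. It requires monitoring until the liver values and clinical signs return to normal or baseline, or for as long as medically indicated. It also requires the investigator to "Investigate the etiology of the event and perform diagnostic investigations as medically indicated", and to report an SAE if the case becomes serious.

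A 5 states that it covers every case in which PHL criteria are met. It contains the decision on whether Hy's Law is met, the SAE report when no cause other than the drug is found, and a default SAE report when the needed information is delayed by more than 3 weeks.

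**The concern.** Every patient who reaches A 7 meets PHL criteria, yet one of its branches hands the patient to the section written for those who do not. An investigator with a repeat episode would naturally turn to A 7, because it is the specific rule and says that its own question decides whether the repeat is followed up, reviewed and assessed. Taken literally, the 'No' answer leads to laboratory follow-up and does not mention the etiology work-up in A 4.2 or the Hy's Law decision in A 5.

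The A 5 step matters for reporting. Under Section 6.4.7, deterioration in a protocol-mandated laboratory value is reported as an AE only if it meets an SAE criterion or is the reason for stopping treatment. AST, ALT and total bilirubin are mandated tests (Table 9). A 5 supplies the medically important criterion that makes an otherwise non-serious Hy's Law case reportable, and A 4.1 does not lead there.

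**Working it through.** No arithmetic applies, and the plan states no figure to reproduce. The check sets the scope of A 7 against the entry conditions of the sections it could point to.

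1. **Who is in A 7.** The patient meets PHL criteria now and met them at an earlier on-treatment visit.

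2. **Who is in A 4.1.** Patients who do not meet PHL criteria. No A 7 patient satisfies this condition, so the 'No' branch names a section that cannot apply to anyone sent there.

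3. **Who is in A 4.2 and A 5.** Patients who meet PHL criteria. Every A 7 patient satisfies both conditions.

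4. **What the literal pointer leaves out.** A 4.1 refers to the protocol's laboratory guidance. For chemistry, that is an early repeat of clinically significant abnormal results, preferably within 24 to 48 hours (Section 6.3.1), and the per-cycle panel in Table 1. Neither contains an etiology work-up or a Hy's Law decision.

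5. **How the branches rank.** The 'Yes, significant change' branch goes to A 4, which resolves to A 4.2 for a patient who meets PHL criteria. The 'No' branch goes to A 4.1. So a repeat whose earlier episode was not attributed to the disease under study or to pre-treatment elevation gets a lighter process than a changed repeat with one of those explanations. An earlier episode attributed to another drug is one plain 'No' case.

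6. **A related reference.** The 'significant change' bullet in A 6 points to Appendix B 5. That section is general guidance on important medical events and contains no PHL process. Two faulty references in adjoining sections suggest cross-reference errors and not an intended rule.

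**The case against.** The strongest defence is that A 7 is a deliberate exception, since it says that handling of a repeat depends on the cause found earlier. This does not hold. A 4.1 excludes these patients by its own condition, and the exception would lighten follow-up where the earlier episode lacked the two explanations that A 7 asks about.

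A second defence is that other rules fill the gap, and much of this stands:

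- A 1 calls for joint review of cases meeting PHL criteria, and A 3 for prompt review of each new laboratory report.
- A 5 claims all such cases.
- The note under Table 9 in Section 6.3.1 sends patients with the combined elevations to Appendix A.
- Section 6.4.8 says liver biochemistry elevations require further evaluation and that the combined elevations may need SAE reporting. It is not limited to first episodes.
- Section 6.5.1 requires any SAE to be reported within 24 hours, whichever branch was taken.
- A 1 also says the appendix is not a full guide to managing raised liver values.

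A reader might therefore go too far in three ways:

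- **That 'No' cases will go unassessed or unreported.** The rules above still bind, so the documents do not support this.
- **That 28-day cycles leave the patient untested beyond the 3-week limit in A 5.** That limit concerns delay in gathering the information needed to classify a case. It is not a testing interval, and Section 6.3.1 asks for an early repeat test.
- **That the 'Yes, significant change' pointer is equally wrong.** A 4.1 and A 4.2 sort patients by their own conditions, so a reference to A 4 already leads to A 4.2, and A 5 applies as well.

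**Conclusion.** The point holds as a contradictory safety instruction. The 'No' branch of A 7 names a section that cannot apply to its patients and conflicts with A 4.2 and A 5. A careful investigator may still reach the right process, because A 4.2 is the next heading and A 5 covers the case in its own words. The instruction should not depend on that.

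The size is small in numbers. The documents give no rate of PHL episodes or of repeats, so no probability can be stated; that few patients will be affected is a judgement. No sample size, power figure or efficacy result changes. The point is worth correcting because it concerns possible serious drug-induced liver injury, where the consequence for one patient could be serious. The conclusion rests only on the wording of Appendix A and on reading A 7 as the rule an investigator would consult for a repeat episode.

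The A 6 reference is a lesser matter. It is misdirected but sets no contrary rule.

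**What to change.** In the A 7 'No' branch, replace the reference to A 4.1 with A 4.2 and A 5. In the A 6 'significant change' bullet, replace Appendix B 5 with A 4.2 and A 5. The 'Yes' branch of A 7 needs no correction.

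The cost is two corrected references in the next amendment, with no change to visits, samples or analyses.
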